#### Secondary Endpoints:

1. Overall Response Rate (ORR) achieved at 12 months.
2. Progression Free Survival.
3. Response Duration.
4. Rate of negative Minimal residual disease (MRD) at 12 months, time to obtain a molecular response, duration of molecular response. Prognostic value of MRD status.
5. Overall survival.
6. Rates of AEs, SAEs and SUSARs by CTC grade (Version 4.03) during I+R treatment.
7. To assess the health-related quality of life (QOL) during treatment.
8. Genomic studies in indolent clinical forms of MCL (IGHV mutational status, DNA copy-number and whole exome sequencing).

### 5.2 STUDY DEVELOPMENT

All data of patients included in the study will be collected in the case report form (CRF).

The active monitoring of patients includes anamnesis, physical examination, laboratory tests, ECOG status, vital signs, adverse events assessment and concomitant medication.

Data on adverse events and concomitant medications will be collected up to 30 days after the last study medication administration. In the case of serious adverse events (and related concomitant medication) registration should be extended until the SAE is resolved or is considered as clinically stable by medical judgment.

When a patient **terminates study or terminate study treatment due to disease progression**, ~~finalizes protocol procedures, no additional diagnostic tests will be performed,~~ only survival and progression/relapse data will be collected **(when applicable) until the end of the study as described in section 5.2.6**. The study is divided into 3 phases: a Screening phase, a Treatment Phase, and a Treatment and Follow-up phase.

Tests and evaluations to be performed in different periods of the study are detailed below.

**Version 3.2: September 16th, 2020**

### 5.2.1 Screening Phase:

Within a maximum of 28 days\* prior to treatment initiation, it should be determined and collected the following clinical and laboratory data:

- Informed consent.
- Date of birth, date of diagnosis, medical history and concomitant medication.
- Physical examination, ECOG and vital signs.
- Quality of Life questionnaires.
- Local laboratory pathology diagnosis. The tissue FFPE block or slides will be sent to the central pathology laboratory to confirm the diagnosis and the Ki-67 proliferation rate whenever possible. The timeline of 28 days for the central review is not strict.
- CBC (hemoglobin, leucocytes with differential count and platelets).
- Biochemistry: creatinine, urea, uric acid, Na, K, Ca, glucose, total protein, protein electrophoresis, albumin, IgG assessment, IgA and IgM, bilirubin, alkaline phosphatase, GGT, AST, ALT, LDH and  $\beta_2$  seric microglobulin, serum immunofixation.
- Coagulation; TP, TTP, fibrinogen.
- Pregnancy test (performed on blood or urine) in women of childbearing potential.
- Hepatitis B and C (including anti-core VBH) and HIV serology.
- Disease assessment by PET/CT.
- Electrocardiogram.
- Left ventricular ejection fraction (optional, only mandatory in patients with a history of heart disease).
- Bone marrow biopsy.
- Bone marrow aspirate (with local study by flow cytometry and sending to MRD determination) ~~is optional, but recommended in cases exclusively involving bone marrow and peripheral blood.~~
- Concomitant medication.
- Tumor samples for molecular sub-study and MRD study. It will be obtained 30-50 ml of peripheral blood for shipment to central laboratory. Other territories will be considered based on clinical presentation, availability of samples (exceeding from diagnosis) and method of sample preservation.

\* Baseline laboratory should be performed within 7 prior days at the most. The PET-CT and BMB obtained within 3 and 6 months prior to enrolment in the study respectively, will be accepted as a baseline examination in patients who meet study eligibility criteria. A broader interval may be considered for these baseline tests according to specific cases

\*\* If the central review does not confirm the pathological diagnosis, the patient must be withdrawn from the study.

Version 3.2: September 16th, 2020

### 5.2.2 Study procedures during treatment phase

#### 5.2.2.1 Before each treatment cycle (monthly the first year of treatment, thereafter every 3 months):

- Anamnesis, physical examination, ECOG, vital signs.
- Biochemistry and CBC.
- Adverse events and Concomitant medication

**5.2.2.2 At 6 months from treatment initiation, in addition to states in section 5.2.2.1 “before each treatment cycle”, when applicable:**

- CT scan of chest, abdomen, pelvis and other involved sites if applicable
- Consider bone marrow aspirate (with study by flow cytometry) in forms with exclusively marrow involvement and peripheral blood at diagnosis.
- Assessing of minimal residual disease (MRD) in peripheral blood by RQ-PCR.

**5.2.2.3 At 12 months from treatment initiation in addition to states in section 5.2.2.1 “before each treatment cycle”, when applicable:**

- Quality of Life questionnaires.
- PET/CT.
- Bone marrow biopsy.
- ~~Optional~~: Bone marrow aspirate (with local study by flow cytometry and sending for MRD determination).
- Minimal residual disease (MRD) in peripheral blood assessment by RQ-PCR.

Version 3.2: September 16th, 2020

**5.2.3. Treatment and Follow-up Phase**

From month 12 or from completion of treatment without disease progression and up to 7 4 years from patient inclusion in addition to states in section 5.2.2.1 “before each treatment cycle”, when applicable:

- CT scan every 6 months.
- Minimal residual disease (MRD) in peripheral blood assessment by RQ-PCR every 6 months.

Version 3.2: September 16th, 2020

**5.2.4 End of Study Visit (30+/- 5 days)**

An End of ~~Treatment~~Study Visit will be scheduled within 30 days after the last dose of study drug for all subjects, except for reasons of death or withdrawal of consent for study participation. (see section 5.2.5)

Version 3.2: September 16th, 2020

The following procedures will apply:

- Anamnesis, physical examination, ECOG status and vital signs.
- Quality of life questionnaires.
- CBC, biochemistry.
- Adverse events and concomitant medication.
- CT scan (not necessary if the previous determination was obtained within the last three months and there is no clinical change that justifies it).
  - Minimal residual disease (MRD) in peripheral blood assessment by RQ-PCR (not necessary if the previous determination was obtained within the last three months and there is no clinical change that justifies it).
  - Obtain new tumor sample from peripheral blood, when applicable (in case of progression or relapse).

### 5.2.5. End of study

Participation in the study will end when any of the following occurs:

- The patient completes 7 years of treatment or follow-up since inclusion in the study,
- Progression during treatment or in the follow-up phase,
- Loss of follow-up or death
- Withdrawal of consent by the patient during the treatment or follow-up phase

Version 3.2: September 16th, 2020

### 5.2.6 Follow-up post-progression or End of Study

**Follow-up by routine clinical practice of progression (if applicable) and / or survival (alive / death / loss to follow-up) until trial closure** ~~Overall Survival follow-up (Live/Dead/lost of follow-up).~~

## 5.3 RESPONSE AND TOXICITY CRITERIA

Treatment response will be assessed according to the International Response Criteria for Non-Hodgkin Lymphoma (13).

### 5.3.1 Response definitions

The response obtained will be classified according to the 2014 criteria of Cheson et al. (13) (see Annex VII). The PET / CT will be reviewed by GELTAMO PET platform.

### 5.3.2 Response assessment:

Percentage of complete remissions at 12 months: is defined as the percentage of patients who are alive and in complete response at 12 months from the date of treatment initiation. All patients will be evaluated with PET- CT and bone marrow biopsy at that time.

Overall response rate: Proportion of patients who experienced PR or CR.

Progression free survival (PFS): defined as the time between start of treatment and the first documentation of recurrence, progression, or death in the event of no documented recurrence, or start of a new anti – lymphoma treatment, due a refractory or persistent disease.

Response duration: is defined as the time from the documentation of tumor response to disease progression or death, in the event of no documented recurrence, or start of a new anti – lymphoma treatment because of refractory or persistent disease.

Overall survival (OS): is defined as the time between the start of treatment and death from any cause. Patients that are withdrawn from the trial or lost of follow-up, will be censored with the date of last contact. Patients who are still alive at the end of the study will be censored at that time.

Minimal residual disease negative rate: is defined as the proportion of subjects who are MRD negative (ie, less than the lower limit of detection for the MRD assay). All patients with a valid MRD result (negative or positive) will be included in this analysis.

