Secondary Endpoints	
 
1. To determine the overall response rate (ORR) at 12 months, Progression free survival (PFS), duration of response (DOR) and overall survival (OS).
 
2. To determine the rate of negative minimal residual disease (MRD), the time to obtain a molecular response and the median duration of the molecular response in I+R responding patients.
 
3. Rates of AEs, SAEs, and SUSARs by CTC grade (Version 4.03) during I+R treatment
 
4. To assess the health-related quality of life (QOL) during treatment.
 
5. Genomic studies in indolent clinical forms of MCL (IGHV mutational status, DNA copy-number and whole exome sequencing).
 

Sample Size	
First Stage: 15 patients
 
Second Stage: If at least 6 patients show a complete response during first stage, the study will continue until inclusion of 50 patients.

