### 3.6 TREATMENT WITHDRAWAL CRITERIA

In the event of sustained negative MRD (at least 6 months) after 2 years of continuous treatment, the investigator should withdraw ibrutinib treatment.

In addition, the investigator, for reasons of medical urgency, must withdraw the patient from the study treatment according to the following criteria:

1. Disease Progression: Patients that present progression will discontinue the treatment
2. Unacceptable toxicity
- ~~3. Negative MRD at least for 6 months after 2 years of treatment~~

**3.4. Patient non-compliance** ~~Investigator decision~~

**4.5.** Patient rejection to continue study treatment

Patients who complete treatment will undergo the end-of-treatment testing and evaluation schedule as described in section 5.2.4

Version 3.2: September 16th, 2020

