## 4. PATIENT ELIGIBILITY CRITERIA

### 4.1 INCLUSION CRITERIA

1. Subjects with confirmed diagnosis of Mantle Cell Lymphoma (World Health Organization Classification, WHO 2008). Classical, small-cell variants and marginal-zone variants can be included.
2. Age 18 years or older.
3. Subjects must not have received any prior therapies (excluding diagnostic splenectomy).
4. Asymptomatic patients.
5. Ann Arbor clinical stages I-IV.
6. Eastern Cooperative Oncology Group (ECOG) performance status <2 (0-1).
7. Subjects with a non-nodal MCL presentation with mainly bone marrow or peripheral blood involvement.
8. Other asymptomatic clinical presentations are acceptable in case of low tumor burden, including nodal MCL with lymph node enlargement  $\leq 3$  cm in the maximum diameter and with low proliferation index (Ki-67  $\leq 30\%$ ).
9. The following laboratory values at screening:
  - Neutrophil count  $\geq 1 \times 10^9/L$ , Hemoglobin level  $\geq 100$  g/L or platelet count  $\geq 100 \times 10^9/L$
  - Transaminases (AST and ALT)  $\leq 3 \times$  ULN
  - Total bilirubin  $\leq 1.5 \times$  ULN unless bilirubin rise is due to Gilbert's syndrome or of non-hepatic origin
  - Creatinine  $\leq 2 \times$  ULN or calculated creatinine clearance  $\geq 40$  mL/min/1.73m^2
10. Stable disease without evidence of clinical progression criteria for at least 3 months. Patients in prolonged therapeutic abstention may be included.
11. Women of childbearing potential and men who are sexually active must be practicing a highly effective method of birth control during and after the study consistent with local regulations regarding the use of birth control methods for subjects participating in clinical trials. Men must agree to not donate sperm during and after the study. For females, these restrictions apply for 1 month after the last dose of study drug. For males, these restrictions apply for 3 months after the last dose of study drug.
12. Women of childbearing potential must have a negative serum (beta-human chorionic gonadotropin [ $\beta$ -hCG]) or urine pregnancy test at Screening. Women who are pregnant or breastfeeding are ineligible for this study.
13. Sign (or their legally-acceptable representatives must sign) an informed consent document indicating that they understand the purpose of and procedures required for the study, including biomarkers, and are willing to participate in the study.

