## **8. MOLECULAR SUB-STUDY**

Peripheral blood samples will be collected prior the start of therapy in order to obtain DNA and RNA purified of tumor samples and DNA and RNA of paired non tumor samples. IGHV mutational assessment and genomic studies including whole exome sequencing (WES) and the analysis of DNA copy number alterations will be conducted in those pretreatment samples.

Lymph node or other tissue biopsies (either frozen or FFPE tissue) diagnostic of MCL will be collected when available to perform histological review, create a TMA and to obtain tumor DNA and RNA in order to expand the genomic studies especially in those cases without peripheral blood involvement.

A new tumor sample collection either in peripheral blood and/or tissue will be obtained whenever possible in those patients presenting progressive or relapsed disease to I+R in order to allow conducting second time-point WES studies. These studies will focus particularly in the study of the mechanisms of ibrutinib resistance.

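### The MRD-negative rate in Section 5.3.2 requires no clone detectable at baseline, so patients whose blood was never positive can count as MRD negative

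*Protocol*

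**What the plan says.** Section 5.3.2 fixes both parts of the rate. The numerator rule is that it "is defined as the proportion of subjects who are MRD negative (ie, less than the lower limit of detection for the MRD assay"). The denominator rule is "All patients with a valid MRD result (negative or positive) will be included in this analysis". The word valid is explained only by that bracket.

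Section 5.1 lists the secondary MRD endpoints as "Rate of negative Minimal residual disease (MRD) at 12 months, time to obtain a molecular response, duration of molecular response", and adds the prognostic value of MRD status. The synopsis describes the two time-related endpoints as "the time to obtain a molecular response and the median duration of the molecular response in I+R responding patients". Molecular response is not defined anywhere in the protocol.

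On the population, inclusion criterion 8 in Section 4.1 reads "Other asymptomatic clinical presentations are acceptable in case of low tumor burden, including nodal MCL with lymph node enlargement", up to a stated size and proliferation limit. It asks for no blood involvement. Section 8 plans to use tissue to extend the genomic work "especially in those cases without peripheral blood involvement".

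On sampling, blood RQ-PCR is scheduled at months 6 and 12 (Sections 5.2.2.2 and 5.2.2.3). After that, Section 5.2.3 specifies "Minimal residual disease (MRD) in peripheral blood assessment by RQ-PCR every 6 months". The procedures table in Section 5.5 also schedules a screening blood MRD test, marked as the initial study, and no endpoint definition uses it. Section 5.2.1 allows baseline samples from sites other than blood.

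**The concern.** An MRD-negative rate is read as evidence that treatment cleared a detectable clone. That reading holds only if the clone could be detected beforehand in the compartment being tested. In a patient with low-burden nodal disease the clonal marker may come from node or marrow. The blood assay can then give a valid result below the detection limit at screening, month 6 and month 12. Section 5.3.2 scores that patient as MRD negative, exactly like a patient whose blood was positive and became negative.

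The rate would then depend partly on how many nodal patients were enrolled and not only on the effect of ibrutinib plus rituximab. If the same negativity rule is used for molecular response, time to response, its duration and the prognostic analysis would all mix patients who were never positive with patients who cleared.

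**Working it through.** The protocol states no target, sample size or power for any MRD endpoint, so there is no figure to reproduce. The check has two parts.

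**1. Does the text allow it?**

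- Numerator (5.3.2): any result below the detection limit, with no baseline condition.
- Denominator (5.3.2): all valid results, negative or positive, with no baseline condition.
- Population (4.1 criterion 8; Section 8): patients without blood involvement are eligible and expected. Section 2.1 says that blood is often involved in MCL but gives no percentage.
- Marker source (5.2.1): baseline samples may come from sites other than blood.
- Follow-up compartment (5.2.2.2, 5.2.2.3, 5.2.3, table in 5.5): blood throughout. Marrow is also sent for MRD at screening and month 12. Section 5.3.2 does not say which compartment decides status.
- Synopsis restriction to responders: this concerns response to I+R, not baseline MRD. A nodal responder whose blood was always negative still enters.

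Nothing in the text removes a never-positive patient from the numerator.

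**2. How large could the effect be?**

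Let f be the share of assessed patients with no clone detectable in blood at baseline but a valid follow-up assay. Let c be the true clearance rate among the rest. Assume that never-positive patients stay negative to month 12.

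- Rate under 5.3.2 = f + (1 - f) x c
- Rate among patients positive at baseline = c
- Excess = f + (1 - f) x c - c = f x (1 - c)

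Both f and c are assumptions. With the planned 50 patients, all assessed, the cells show the rate under 5.3.2 with the excess in points in brackets:

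| f (patients) | c = 30% | c = 50% | c = 70% |
|---|---|---|---|
| 10% (5) | 37% (7) | 55% (5) | 73% (3) |
| 20% (10) | 44% (14) | 60% (10) | 76% (6) |
| 30% (15) | 51% (21) | 65% (15) | 79% (9) |
| 40% (20) | 58% (28) | 70% (20) | 82% (12) |

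Example: f = 20% and c = 50% give (10 + 0.5 x 40) / 50 = 30/50 = 60%, against a true clearance of 50%. The excess runs from 0.10 x 0.30 = 3 points to 0.40 x 0.70 = 28 points. It is never negative. If no patient cleared (c = 0), the reported rate would still equal f.

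**The case against.** The strongest reply is that whether a patient with no clone in baseline blood gets a valid follow-up result depends on assay rules. Those may sit in a laboratory manual or an analysis plan that is not at hand. The remark in Section 8 is about tissue for genomic studies, and it does not say that those patients are RQ-PCR negative in blood. Criterion 7 admits mainly marrow or blood presentations, so f could be close to zero. The trial is exploratory, and MRD is a secondary family with no formal test.

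Much of this stands as a limit on size. It does not remove the point: Section 5.3.2 sets the numerator and denominator itself and explains valid only as negative or positive. Excluding patients without any marker would still leave in those whose marker came from node or marrow.

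Several stronger readings are tempting but are not supported:

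- *Section 3.6 contradicts Section 3.3 on stopping ibrutinib.* It does not. Section 3.3 carries the same MRD discontinuation sentence, as do the synopsis and Section 3.4.1.
- *A never-positive patient meets the withdrawal condition from the start.* Section 3.6 reads "In the event of sustained negative MRD (at least 6 months) after 2 years of continuous treatment, the investigator should withdraw ibrutinib treatment", so the two-year condition applies first. Progression is a separate criterion in the same section.
- *The protocol declares such patients molecular responders at their first visit.* Molecular response has no definition, so carrying the negativity rule over to time and duration is an inference.
- *Marrow can replace blood throughout.* The month-6 aspirate concerns only forms confined to marrow and blood, and no marrow is scheduled after month 12.

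**Conclusion.** The point holds for the MRD-negative rate. As written, Section 5.3.2 can count patients whose blood was never positive as MRD negative, and the resulting bias can only be upward. Its size is f x (1 - c), which is 3 to 28 points for f of 10 to 40% and c of 30 to 70%. These ranges are illustrative, because the protocol gives neither quantity. The result also assumes that some blood-negative patients have a marker from another site and therefore a valid blood assay.

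For time to and duration of molecular response, and for the prognostic analysis, the problem is conditional on the same negativity rule being applied. The primary complete remission endpoint and the two-stage rule do not depend on it. It is a cheap and worthwhile correction to a stated definition of a secondary endpoint.

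A narrower consequence remains for treatment. The synopsis and Sections 3.3, 3.4.1 and 3.6 rely on negative MRD without naming a compartment or a baseline condition.

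**What to change.** In Section 5.3.2:

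- Restrict the MRD-negative rate, and time to and duration of molecular response, to patients with a clone detectable at screening in the compartment followed. The screening blood MRD test in the Section 5.5 table supplies this.
- Define molecular response explicitly on that basis.
- Report blood as the longitudinal measure, and marrow MRD separately at screening and month 12.
- List baseline-negative patients separately as not assessable for molecular response.

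The sponsor should also reconcile what negative MRD means in the synopsis and Sections 3.3, 3.4.1 and 3.6 with Section 5.3.2. No clinical rule is proposed here.

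No new sampling is needed. The cost is a smaller denominator, a wider interval and possibly a lower reported rate. At f = 20% and c = 50%, 40 of 50 patients remain. The approximate 95% half-width goes from 1.96 x sqrt(0.6 x 0.4 / 50) = 13.6 points around 60% to 1.96 x sqrt(0.5 x 0.5 / 40) = 15.5 points around 50%.

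### The 12-month MRD-negative rate is taken only over patients with a valid MRD result, so deaths, losses and probably progressions before month 12 leave the denominator, which can inflate the rate

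*Protocol*

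**What the plan says.** Section 5.3.2 of the protocol calls a patient MRD-negative when the result is below the assay's detection limit. It then fixes who is analysed: "All patients with a valid MRD result (negative or positive) will be included in this analysis". It names no time point and gives no rule for a patient without a result. The time point is in the secondary endpoints of section 5.1: "Rate of negative Minimal residual disease (MRD) at 12 months".

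These parts of the protocol decide who can have a month-12 result:

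- **Progression.** Section 5.2.5 lists "Progression during treatment or in the follow-up phase" among the events that end participation, together with death, loss to follow-up and withdrawn consent. Section 5.2 adds that once a patient ends the study, or ends treatment for progression, "only survival and progression/relapse data will be collected".
- **Stopping without progression.** Section 5.2.3 keeps these patients in six-monthly MRD sampling. The synopsis (study procedures, part D) says that scheduled evaluations go on after the end-of-treatment visit.
- **End-of-treatment visit.** Section 5.2.4 includes an MRD test about 30 days after the last dose for everyone except those who died or withdrew consent. The test may be skipped if one was done in the previous three months and nothing has changed clinically.

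In the same section 5.3.2, the 12-month CR rate "is defined as the percentage of patients who are alive and in complete response at 12 months from the date of treatment initiation". The synopsis lists the MRD rate together with "the median duration of the molecular response in I+R responding patients", and it is unclear whether the restriction to responders also applies to the rate.

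**The concern.** Whether a month-12 result exists depends partly on how the patient has done. Patients who die or progress in the first year are treatment failures, and they are the ones with no month-12 sample scheduled. Under the stated rule they are dropped; they do not count as not negative.

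The rate then answers a narrower question: how often MRD is undetectable among patients still being sampled at one year. A reader of a single-arm report is likely to take it as the share of treated patients who reach MRD negativity. It would also stand beside a 12-month CR rate that requires the patient to be alive. A patient who dies in month 8 cannot count as a CR, but disappears from the MRD rate.

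The denominator is written into the protocol, so an analysis plan that follows the protocol would inherit it.

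**Working it through.** **Step 1: who has a result that can count at month 12.** Reading sections 5.1, 5.2, 5.2.3, 5.2.4, 5.2.5 and 5.3.2 and the synopsis together:

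| Patient before month 12 | MRD sample at month 12 | Under the stated rule |
|---|---|---|
| Still on treatment, no progression | Scheduled | Counted |
| Stopped treatment, no progression | Six-monthly sampling continues | Counted |
| Progressed | None scheduled; possibly an end-of-treatment sample | Dropped, unless that sample counts (not stated) |
| Died | None | Dropped |
| Withdrew consent or lost to follow-up | None | Dropped |
| Sampled, but the assay failed | No valid result | Dropped |

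Rows 3 and 4 are linked to poor outcome. Row 5 may or may not be. Row 6 need not be.

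**Step 2: inputs.** The protocol gives no expected MRD-negative rate and no expected number of patients without a result, so there is no planned figure to reproduce. Section 7 plans N = 50 patients with at least 46 evaluable for response, which allows for 50 − 46 = 4 non-evaluable patients. I use m = 4 only as a convenient size: that allowance concerns evaluability for response and does not forecast deaths or progressions. The number of MRD-negative patients, k, is assumed.

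**Step 3: outcome-related losses.** If all m patients without a result are truly not negative:

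- valid-result rate = k / (N − m)
- all-treated rate = k / N
- ratio = N / (N − m) = 50/46 = 1.087

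| k (assumed) | k/46 | k/50 | Difference |
|---|---|---|---|
| 25 | 54.3% | 50.0% | 4.3 points |
| 30 | 65.2% | 60.0% | 5.2 points |
| 35 | 76.1% | 70.0% | 6.1 points |
| 40 | 87.0% | 80.0% | 7.0 points |

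With m = 2 and k = 30, the figures are 30/48 = 62.5% against 60.0%, a difference of 2.5 points.

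**Step 4: technical losses.** Suppose instead that the 4 missing results are unrelated to outcome. The valid-result rate 30/46 = 65.2% then has no expected bias. Counting the 4 as not negative gives 30/50 = 60.0%, which is 5.2 points too low in expectation.

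**Step 5: limits.** With 30 negatives among 46 valid results, the share of all 50 patients who are truly negative lies between 30/50 = 60.0% (none of the 4 negative) and 34/50 = 68.0% (all 4 negative). The valid-result figure of 65.2% is inside this range. Where the truth lies depends on why the 4 are missing, so those reasons have to be reported.

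**The case against.** The case for leaving the text alone has weight. Section 5.3.2 states its analysis set openly, and an assay-based endpoint may reasonably use patients with an assay result. The patients are asymptomatic, stable for at least three months and have Ki-67 of at most 30%, so few may die or progress within a year. The endpoint is one of several secondary ones in an exploratory phase II trial, and no test or stage-one rule depends on it. All of this stands. It limits the size and importance of the point, but does not change how early deaths and progressions are handled.

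A reader might infer more than the protocol supports:

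- *That everyone who stops treatment early is lost from the rate.* This is not so. Section 5.2.3 and the synopsis keep patients who stop without progression in MRD sampling.
- *That every progressor is certainly excluded.* The end-of-treatment visit can yield an MRD result. Section 5.3.2 names no time point, so whether that result counts is open.
- *That inflation is automatic.* Step 4 shows that results missing for technical reasons give no expected upward bias.
- *That the inflation is large.* Reaching 75% against 60% (30/40 against 30/50) needs 10 of 50 patients lost for outcome-related reasons within a year, and nothing in the protocol supports that number.
- *That the MRD rate contradicts the primary endpoint.* The two treat a death differently, but the denominator of the CR rate is not spelled out either: section 5.3.2 speaks of patients and section 7 of patients evaluable for response. The reporting is uneven, but this is not a contradiction.

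**Conclusion.** The point holds in a limited form. As written, the 12-month MRD-negative rate leaves out patients who die, withdraw consent or are lost before month 12. It also leaves out those who progress before month 12, unless their end-of-treatment sample is accepted. Where the losses reflect failure, leaving them out can only raise the rate.

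The size cannot be fixed from the protocol. If 4 of 50 patients were lost in this way and none was truly negative, the overstatement would be a factor of 1.087, or 4.3 to 7.0 points for all-treated rates of 50% to 80%. Both the number lost and the rates are assumptions. If the losses are purely technical, the expected overstatement is zero.

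The CR test, the stage-one rule and the sample size are not touched. The point is worth acting on because the correction is cheap, not because the trial's main conclusion depends on it.

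**What to change.** In section 5.3.2:

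1. Define the 12-month MRD-negative rate over all treated patients with a trackable MRD marker at baseline. Count death, progression or a missing 12-month result as not negative. Give the same rate over all treated patients.
2. List assay and sample failures separately, so that a reader can tell them from clinical failures.
3. State whether an end-of-treatment sample counts toward month 12.
4. Keep the valid-result rate as a labelled supportive figure.
5. Say in the synopsis whether the reference to responding patients covers the MRD rate or only the duration of molecular response, so that it agrees with section 5.3.2.

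The cost is a few sentences and an extra table column, with no new sampling. The headline rate becomes slightly less favourable, and it is somewhat understated to the extent that technical failures are counted as not negative. Items 2 and 4 let the reader see by how much.
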